## 9.2 PROPOSED ANALYSES

**WP1.** We will assess data quality before analysis, including internal consistency, outliers and missing data. Depending on the proportion of missing data, variables will be either excluded or completed with multiple imputation/other data imputation techniques which may be appropriate. Sensitivity analyses will be used to assess the impact of missing outcome data. We will minimise type 1 errors by applying a full analytics machine learning approach with standard approaches for model training and validation, rather than relying solely on statistical hypothesis testing and arbitrary p-value thresholding.

We will first investigate unadjusted associations between the 2 independent categorical variables (i.e. GA, (S)IMD quintile) and dependent variables (moderate to severe neurodevelopmental impairment at 2 years and academic attainment, defined in 4.1.3.3). We will use univariable statistical learning models to estimate the probability of having an adverse outcome: model 1, GA at birth; model 2, (S)IMD quintile (possible interactions between (S)IMD and GA at birth ([S]IMD x GA) will be tested). Then, a multivariable regression that includes the independent variables and significant interaction terms will be used to investigate associations after mutual adjustment for potential confounding variables/effect modifiers, including parental ethnicity and others listed in 4.1.3. Results will be reported as odds ratios with 95% CIs.

We will apply machine learning methods including feature selection and statistical mapping algorithms. Indicatively, we will use both filter feature selection approaches and embedded feature selection, e.g. the random forest feature importance scores to determine the most parsimonious model comprising a robust feature subset with maximally predictive performance using standard model validation approaches (e.g. k-fold cross-validation). We have previously shown that this approach determines predictors of language impairment in preterm infants with high accuracy. Here, we envisage it will determine the PTB-RFs that jointly contribute, in descending order of importance, to neurodevelopment and educational outcome measures. We will apply partial dependence plots to gain further insights into how specific changes in variable values affect outcomes, and we will explore two-dimensional data representations (e.g., applying t-distributed stochastic neighbour embedding) to visualize data both using the original high-dimensional space and using feature subsets determined using feature selection algorithms. This approach will provide a clear demonstration of the effect of PTB-RFs inherently as part of the statistical model used, including direction of effect as a function of different outcome values, thus accounting for mediation.

**WP2.** Image processing will be carried out using established pipelines for morphometric similarity networks (MSNs), hierarchical complexity (HC) and using in-house techniques for MTsat. There are two statistical approaches. The first will use multivariate statistics in a predictive framework to test whether PTB-RFs are associated with MSNs (brain age), HC (connectome architecture), and MTsat (a marker of myelination). The second will use mediation analyses within a structural equation modelling framework to investigate the role of neuroendocrine stress activation and chronic inflammation as mediators of PTB-RFs on features of EoP. This simultaneously characterises associations among HPA axis activation/DNAm, PTB-RFs, and brain features, and specifically tests the hypothesis that stress and/or chronic inflammation partly and significantly mediate associations between PTB-RFs and brain development.

**WP3.** fMRI data will be pre-processed using fMRIPrep. A general-linear model will be used to analyse BOLD activity of each participant. Individual functional regions of interest (ROIs) will be defined as the 80 voxels within targeted search spaces (for social, attention, and language networks) that have the highest contrast values (i.e., are most similar to the adult timecourse), using a split-half approach such that extraction of response time courses and ROI definition occur in independent data. Functional maturity of each ROI will be calculated as the correlation between each child's (split-half) timecourse and the average adult timecourse; inter-region correlations will be calculated as the average correlation between timecourses across ROIs within each network. These measures capture region-specific functional maturity and the functional coherence of each network. To ensure unpredicted effects do not go undetected in such a valuable dataset, additional measures of brain development, including the response magnitude to domain-relevant scenes will be explored. Whole-brain random effects analyses will be conducted to identify any regions that are differentially recruited during domain-relevant scenes

relative to control scenes in preterm children as compared to term-born children. We will explore the impact of preterm birth on response time courses for attention and language, as well as social networks. These analyses will be corrected for multiple comparisons by estimating the false-positive rate via 5,000 Monte Carlo permutations.

Diffusion images will be pre-processed (realigned, co-registered to the anatomical, and normalised) to reduce distortion, and submitted to eddy-current and motion correction analyses using QSIprep. Diffusion data will be analysed with a tensor model. Tensor model metrics (fractional anisotropy [FA] and mean diffusivity [MD]) are well studied and can be interpreted within a large literature on white matter development. Specific tracts will be identified based on previous work on white matter development and particular cognitive functions (for example, for social cognition, we will focus on the arcuate fasciculus, inferior fronto-occipital fasciculus, and corpus callosum). Average FA and MD will be calculated within tracts that connect individually-defined functional ROIs (as defined above), per network. Additionally, metrics with increased biological specificity from more advanced biophysical models of the diffusion signal will be explored. For example, the NODDI model enables calculating the intracellular volume fraction of water (ICVF) and orientation dispersion index (ODI).

Structural images will be used as anatomical reference for the diffusion and fMRI data. Structural images will be processed using FreeSurfer performing cortical reconstruction and volumetric segmentation. This step will be run inside the QSIprep and fMRIPrep processes.

Linear and mixed effects regressions will be used. Analyses with neuroimaging measures will include participant motion and age as covariates. When multiple statistical tests within a family are conducted, Bonferroni corrections will be applied.

In neuroimaging analyses, we will control type 1 error while minimising the risk of type 2 error by use of family-wise error rate and threshold-free cluster enhancement.

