## Hypotheses

Work package 1:

1) Specific preterm birth associated risk factors (PTB-RFs), which may be clinical/demographic, psychosocial (e.g. maternal stress), or social/infrastructural (e.g. deprivation), modify the relationship between GA at birth and neurodevelopmental and/or educational outcomes

Work package 2:

2i) Atypical activation of the HPA axis leads to EoP, indexed on MRI by dysmaturity (altered chronological brain age), reduced connectome complexity, and biomarkers of hypomyelination

2ii) DNAm proxies of chronic systemic inflammation are present in preterm infants at term equivalent age and are associated with MRI features of EoP.

2iii) The effect of PTB-RFs identified in WP1 on brain development are mediated by alterations in the neonatal HPA axis and/or chronic systemic inflammation.

Work package 3:

3i) Preterm children have domain-specific delays in cognition at school age

3ii) Structure-function networks underpinning cognition are altered in preterm children

3iii) PTB-RFs identified in WP1 predict structural and functional maturity at 5-years

This protocol describes a programme of work packages. Permissions and approvals for each work package will be managed separately. New approvals will be sought for WP1 which will be led and managed by investigators based at Imperial College London. New approvals will also be sought for WP2 which will be led and managed by investigators based at the University of Edinburgh. WP3 already has approvals in place and is managed by University of Edinburgh investigators (Research Ethics

Committee No: 16/SS/0154, NHS Lothian R&D No: 2016/0255). Permissions are not required for WP4. Detailed information about these arrangements can be found in section 12.1 Ethical Conduct.

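### WP1's hypothesis is that several classes of risk factor modify the effect of gestational age, but the plan names only the deprivation interaction and keeps interactions only if significant

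*Protocol*

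**What the plan says.** The Hypotheses section gives WP1 a single hypothesis: that specific risk factors associated with preterm birth "modify the relationship between GA at birth and neurodevelopmental and/or educational outcomes". The factors span three classes: "which may be clinical/demographic, psychosocial (e.g. maternal stress), or social/infrastructural (e.g. deprivation").

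The WP1 part of section 9.2 starts from "the 2 independent categorical variables (i.e. GA, (S)IMD quintile") and fits a model for each. In a parenthesis to the second model it adds that "possible interactions between (S)IMD and GA at birth ([S]IMD x GA) will be tested". No other interaction is named. In the next step "a multivariable regression that includes the independent variables and significant interaction terms will be used", and the remaining factors enter "after mutual adjustment for potential confounding variables/effect modifiers, including parental ethnicity and others listed in 4.1.3". Results are to be odds ratios with 95% confidence intervals. No significance threshold is given for the interaction terms.

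The machine-learning paragraphs of the same section describe feature selection, random-forest importance, partial dependence plots and two-dimensional visualisation. Their stated product is a ranking of the factors that jointly contribute to outcome. Effect modification of GA is not mentioned there.

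**The concern.** A claim that a factor modifies the GA effect is a claim about a product term, or about a contrast of GA effects across levels of the factor. A factor entered only as a main effect leaves the GA odds ratio the same at every level of that factor, whatever the data show. Clinical, demographic and psychosocial factors have no stated product term with GA, so for those classes the written plan yields no estimate that bears on hypothesis 1.

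The one interaction that is named must then pass a significance filter. If it fails, the final model assumes no modification. If it passes, the estimate shown is a selected one, and its 95% interval is computed as though no selection had taken place. At stake are whether WP1 can answer its own hypothesis, and whether the interaction it does report is of the right size.

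**Working it through.** **Hypothesis against analysis**

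| Class in hypothesis 1 | Place in the WP1 regression | GA product term stated? |
|---|---|---|
| Social/infrastructural (deprivation) | (S)IMD quintile, named independent variable | Yes |
| Clinical/demographic | Adjustment variables | None stated |
| Psychosocial (example: maternal stress) | Not named; at most an adjustment variable | None stated |

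The plural interaction terms do not show that more is intended, since quintiles crossed with GA categories already give several terms. Calling the other variables effect modifiers does not turn adjustment into a test of modification. Random forests can absorb interactions, but the section specifies no interaction estimate, contrast by GA or test from them.

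**What the significance filter does**

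WP1 states no power, alpha, effect size or event rate, so there is no figure to reproduce. What follows is an illustration on assumed inputs.

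Inputs from section 9.1: at least 100,000 infants, 2-year outcome for at least 60% (70% in recent years), postcode (the source of the deprivation index) for 90%. Taking exactly 100,000 and independent missingness:

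- 100,000 × 0.60 × 0.90 = 54,000
- 100,000 × 0.70 × 0.90 = 63,000

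Assumptions: one contrast (most against least deprived quintile, 20% of infants each) by a two-group GA split; share g in the lower GA group 20 to 50%; outcome risk p 10 to 30%, equal across cells; Wald test, two-sided 0.05.

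Formulas, with m = ln(OR)/SE and c = 1.96:

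- SE = √[ Σ over four cells of 1/(n_cell · p(1−p)) ]
- Chance of retention = 1 − Φ(c−m) + Φ(−c−m)
- Inflation of the retained log odds ratio = { m + [φ(c−m) − φ(c+m)] / retention } / m
- Coverage among retained 95% intervals, for 0 < m < 2c = [Φ(c) − Φ(c−m)] / retention; for m ≥ 2c = 0.95 / retention

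Worked case: n = 54,000, p = 0.10, g = 0.20, true OR 1.1.

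- Each quintile has 10,800 infants, split 2,160 and 8,640. Multiplied by 0.09 these give 194.4 and 777.6.
- SE = √(2/194.4 + 2/777.6) = 0.113
- m = 0.0953/0.1134 = 0.840
- Retention = 0.1315 + 0.0026 = 0.134
- Inflation = [0.840 + (0.2132 − 0.0079)/0.134]/0.840 = 2.82
- Coverage among retained = 0.1065/0.134 = 79%

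Over the whole assumed range:

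| True interaction OR | Retained | Inflation of log OR if retained | Coverage of retained 95% interval |
|---|---|---|---|
| 1.1 | 13–41% | 1.55–2.82 | 79–94% |
| 1.2 | 36–91% | 1.05–1.64 | 93–97% |
| 1.3 | 64–99.8% | 1.00–1.25 | 95–97% |

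If there is no interaction, a term kept at 0.05 always has a 95% interval that excludes the truth. The damage is therefore concentrated where true modification is absent or small.

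**Why a multiplicity rule is needed once more interactions are fitted**

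With k independent tests at 0.05 the family-wise error is 1 − 0.95^k: 23% for k = 5, 40% for k = 10, 64% for k = 20.

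**The case against.** The strongest reply is that the protocol only outlines the analysis. A list of product terms and a multiplicity method are normally settled in the SAP, which is not at hand. Section 9.2 also refers to further effect modifiers listed in a section 4.1.3, which this document does not contain. A reader might infer that the other GA interactions will never be estimated. The text does not support that: it shows only that they are not specified. What survives is that the protocol fixes one named interaction and a retention rule, and these do not fit its own hypothesis.

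Second, objective 2.1.1 and the WP1 endpoint speak of the contributions of risk factors, which a ranking does deliver. This stands, and it means the misfit could be cured from the other side, by rewording hypothesis 1. It also answers a further inference, that hypotheses 2iii and 3iii would be fed the wrong list. Those hypotheses need risk factors, not modifiers of GA, so the harm does not carry over to them.

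Third, a reader might call the 95% intervals simply invalid. The table does not bear that out: at an interaction odds ratio of 1.3 inflation is slight and coverage holds. The plan also says that it will proceed "rather than relying solely on statistical hypothesis testing and arbitrary p-value thresholding". That statement does not rescue the filter, which is itself a p-value threshold, and one left undefined.

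Some other readings lack support. The label in "We will use univariable statistical learning models to estimate the probability of having an adverse outcome" is loose for a model with an interaction, but nothing says that main effects will be omitted, and the next regression includes both. GA is called categorical, but no bands are given, so a loss of information cannot be shown. The partial dependence plots are not said to be single-variable.

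**Conclusion.** The point holds in this form. As written, the WP1 plan addresses hypothesis 1 for deprivation only. For the clinical/demographic and psychosocial classes it specifies no estimate of modification, in either the regression or the machine-learning step. Keeping interactions on significance exaggerates the retained estimates and undermines the nominal coverage of their intervals, mainly when the true interaction is modest: 1.55- to 2.8-fold on the log scale at an odds ratio of 1.1, at most 1.25-fold at 1.3.

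The mismatch rests on the protocol's text alone. The sizes rest on the assumed risks, group shares, alpha and two-by-two contrast, and would change with the real GA categories. They illustrate the filter's effect and are not a prediction for WP1.

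**What to change.** For each candidate risk factor available in the linked WP1 data, fit a model with GA, the factor, their product and the listed confounders. Report every GA-by-factor interaction with its confidence interval whatever its p-value, and state a multiplicity rule across factors. Delete the rule that keeps only significant interaction terms. Put the list of candidate factors and confounders in the document, since section 4.1.3 is absent.

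Hypothesis 1 should be reworded where a factor is not held in the linked data (the documents do not show that maternal stress is), or if WP1 is really meant to estimate contributions.

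The cost is modest extra analysis and stricter, multiplicity-adjusted thresholds for each interaction. For factors already in the linked records no new data are needed.

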## 2 STUDY OBJECTIVES

### 2.1 OBJECTIVES

The overarching aim of this programme is to determine the biological, psychosocial and socioeconomic PTB-RFs that lead to adverse neurodevelopmental, cognitive, and educational outcomes in children born preterm and to identify the neuroendocrine and epigenetic axes that embed these risks in brain development. This aim will be met through 5 objectives:

2.1.1. Investigate the contributions of multidimensional PTB-RFs to neurodevelopmental and educational outcomes of children born preterm. We will create novel linkages between the National Neonatal Research Database, which contains routine data for ~100,000 infants born in the UK with gestational age (GA) <32 weeks between 01/01/2008-31/12/2019, with education records and neighbourhood deprivation indices. This will determine the relative contributions of demographic, clinical and socioeconomic PTB-RFs to neurodevelopmental and educational outcomes of British children.

2.1.2. Identify the biological axes underlying abnormal brain development in preterm infants. We will characterise brain dysmaturation associated with PTB using neonatal magnetic resonance imaging and use this to investigate the relationship between a) Hypothalamic pituitary-adrenal (HPA) axis activity, and; b) low-level chronic, systemic inflammation indexed by DNA methylation (DNAm), and brain development.

2.1.3. Identify the neural substrates associated with impaired cognitive and behavioural outcomes of preterm children at school age. We will use multiple neuroimaging modalities to identify structural and functional brain networks that predict outcomes (e.g., social development, attention) at 5 years. The contribution of potentially modifiable factors to childhood outcomes, including PTB-RFs identified in the first objective, will be investigated.

2.1.4. Identify neural markers to assess efficacy in future trials of neuroprotective therapies. Our studies linking HPA axis activity, DNAm markers of inflammation and quantitative MRI measures of brain development with outcomes will provide imaging biomarkers that can be used to design and test the efficacy of potential treatments in future studies.

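### WP1 says its machine-learning approach accounts for mediation and minimises type 1 errors; the methods described do neither, so an upstream factor such as deprivation can be ranked low

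*Protocol*

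**What the plan says.** Objective 2.1.1 of the Protocol sets the aim of the WP1 linkage: "This will determine the relative contributions of demographic, clinical and socioeconomic PTB-RFs to neurodevelopmental and educational outcomes of British children". The WP1 endpoint is the weighted contribution of these factors, and it singles out the role of societal as well as clinical factors. Section 1.1 counts both co-morbidities of preterm birth and socioeconomic deprivation among the risk factors.

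Section 9.2 (WP1) then describes two strands.

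- **Regression.** Unadjusted models for gestational age and for (S)IMD quintile come first, with a test of their interaction. A multivariable regression follows, reported as odds ratios with 95% confidence intervals.
- **Machine learning.** The plan reads "Indicatively, we will use both filter feature selection approaches and embedded feature selection, e.g. the random forest feature importance scores", and the target is "the most parsimonious model comprising a robust feature subset with maximally predictive performance using standard model validation approaches". The authors expect that "it will determine the PTB-RFs that jointly contribute, in descending order of importance, to neurodevelopment and educational outcome measures". Partial dependence plots are added to show how changes in a variable affect outcome. The paragraph ends by saying that the approach demonstrates the effect of the risk factors, "including direction of effect as a function of different outcome values, thus accounting for mediation".

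On error control the same section says: "We will minimise type 1 errors by applying a full analytics machine learning approach with standard approaches for model training and validation". The sentence goes on to set this against exclusive dependence on tests and p-value cut-offs, so hypothesis testing is kept alongside.

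The factors identified in WP1 are carried into hypotheses 2iii and 3iii, and into the WP3 subset analyses in Section 9.1.

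**The concern.** Two properties are claimed that the methods do not have.

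The first is mediation. For WP1 the protocol names no mediator, no causal order, and no direct or indirect effect. Selection aims at predictive performance. A partial dependence plot sets one variable to a chosen value and leaves the others as observed. If deprivation acts partly through a neonatal co-morbidity that is also in the model, the plot and the importance score show only what deprivation adds once the co-morbidity is known. The mediated part is assigned to the mediator, not accounted for. A search for a parsimonious subset can go further and drop the upstream factor altogether.

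The second is type 1 error. K-fold validation estimates how well a model predicts unseen cases. It does not fix the probability that an irrelevant factor is selected.

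At stake is the contrast that WP1 exists to inform, social against clinical contribution, and the list of factors that WP2 and WP3 inherit. A reader told that mediation has been accounted for would take a low rank for deprivation as a small overall contribution.

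**Working it through.** WP1 states no power, alpha or effect size, so there is no figure to reproduce. The check has three parts.

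**1. The passages side by side.** For WP2, Section 9.2 specifies mediation analysis within a structural equation model, with named candidate mediators (stress activation and inflammation). For WP3 it specifies permutation-based correction, Bonferroni correction within families and family-wise error control. For WP1 it offers neither kind of tool, yet it claims both results.

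**2. Illustrative simulation of the mediation point.** Every parameter is an assumption; none comes from the protocol. There was one run per setting, with n = 20,000.

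- D is deprivation quintile and d is D standardised. The mediator is M = 0.6d + 0.8e, with e standard normal. C is an independent covariate. Two pure-noise variables are added.
- Log odds of the outcome = −1.8 + bM·M + bD·d + 0.35·C, with bM = s × 0.5/0.6 and bD = (1 − s) × 0.5, where s is the mediated share.
- The total log odds ratio of d is bD + 0.6·bM = 0.5 for every s. The expected direct odds ratio is exp(0.5(1 − s)): 1.65, 1.45, 1.28, 1.13 and 1.00 for s = 0, 0.25, 0.5, 0.75 and 1.
- A 40-tree random forest was fitted on half the data. Permutation importance (loss of AUC) and partial dependence were taken on the other half.

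| Mediated share s | 0 | 0.25 | 0.5 | 0.75 | 1 |
|---|---|---|---|---|---|
| Unadjusted OR of d per SD | 1.66 | 1.64 | 1.58 | 1.60 | 1.59 |
| OR of d given M and C | 1.68 | 1.47 | 1.24 | 1.11 | 1.01 |
| Observed risk difference, Q5 − Q1 | 0.188 | 0.192 | 0.174 | 0.191 | 0.186 |
| Partial dependence difference, Q5 − Q1 | 0.131 | 0.113 | 0.071 | 0.053 | 0.028 |
| Permutation importance of D | 0.117 | 0.077 | 0.020 | 0.010 | 0.001 |
| Rank of D among D, M, C | 1 | 1 | 3 | 3 | 3 |
| Univariable AUC of D | 0.638 | 0.635 | 0.624 | 0.628 | 0.626 |

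The total effect hardly moves. Partial dependence as a fraction of the observed difference falls from 0.131/0.188 = 0.70 to 0.028/0.186 = 0.15. The starting value of 0.70 shows that the forest shrinks the contrast even without mediation, so the relevant comparison is with 0.70 and not with 1. At s = 1 the unrounded importance of D is 0.0014, inside the range seen for the noise variables over all settings (−0.0020 to 0.0015).

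**3. Scale of the multiplicity question.** If m independent null candidates were each tested at an assumed 0.05, the chance of at least one false positive would be 1 − 0.95^m: 40% for m = 10, 64% for m = 20 and 92% for m = 50. This is not the error rate of the planned machine learning, for which no rate is defined. It shows only what a claim to minimise type 1 error would have to address.

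**The case against.** Several points on the other side stand.

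- **Certainty.** A reader might infer that deprivation will be ranked falsely low. The documents do not support that. In the simulation it stayed first at mediated shares of 0 and 0.25. Section 9.2 refers its covariate list to a Section 4.1.3 that is not in the protocol, so the entry of co-morbidities beside deprivation is inferred from Section 1.1 and Objective 2.1.1.
- **The crude association is not lost.** The unadjusted (S)IMD model reports it, and a univariable filter would also keep it (AUC 0.62 to 0.64 throughout). But the unadjusted step covers only gestational age and (S)IMD, and it does not alter the joint ranking.
- **A low conditional rank is not an error.** It is right as a measure of added prediction. It misleads only when read as a total effect, and the mediation clause invites that reading.
- **Type of importance score.** A reader might infer that impurity-based importance will favour variables with many cut points. The protocol gives random forest scores only as an example and does not say which kind, so that inference fails.
- **Type 1 wording.** The sentence concerns machine learning in general, not importance scores or plots in particular. Hypothesis testing is retained beside it, and validation does protect against overfitting. It still sets no false-selection rate.
- **Scope.** Hypothesis 1 is about effect modification, and mediation is tested formally in WP2. A full counterfactual mediation analysis in WP1 is therefore not required. That is a reason to withdraw the claim of mediation, not to leave it in place.

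**Conclusion.** The point holds as a defect in what the protocol asserts, not as detail left to an analysis plan. The statements on mediation and on type 1 error are not supported by the WP1 methods described. If upstream and downstream factors are ranked together, as the protocol's own definition of risk factors suggests, the mediated part of an upstream effect goes to the mediator and the upstream factor can rank low.

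The size is conditional. On the assumed parameters, importance fell about 80-fold (0.117 to 0.0014) between no mediation and full mediation at nearly the same total effect, and the rank changed from a mediated share of 0.5 upward. With a small mediated share, or with no mediators among the features, the ranking would be little affected. The consequence is misreading of the weighted contributions, and of the factors passed to hypotheses 2iii and 3iii. The unadjusted and adjusted regressions remain valid for what they estimate.

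**What to change.** In Section 9.2 (WP1):

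1. Delete the closing clause on mediation. State that importance ranks and partial dependence are conditional and predictive, and are not total effects.
2. For the social-against-clinical contrast, also report each factor's association from models built in temporal order: social and antenatal factors; then gestational age and birth factors; then postnatal factors. Read each factor from the block in which it enters, so that it is not adjusted for its own consequences.
3. Reword the type 1 sentence to say that training and validation guard against overfitting.
4. State a false-selection or selection-stability rule for the risk factors taken into WP2 and WP3.

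The cost is a change of wording, modest extra analysis and an agreed temporal ordering of the candidate factors. No new data are needed.

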**1.2.3 Neural mechanisms of cognitive development in children born preterm:** The neuroprofile of preterm children includes atypical social cognition, attention, memory, and language. An open question is the extent to which these phenotypes are domain-specific, or whether domain-general traits underpin these challenges. For example, resolving whether social difficulties are due to reduced ability

to reason about other peoples' minds versus problems with different aspects of cognition - such as language or attention - is critical for developing mechanistically-informed interventions to promote social development. These alternative accounts cannot be distinguished behaviourally because both lead to impaired performance on behavioural tasks. Functional magnetic resonance imaging (fMRI), however, has potential to clarify the cognitive and neural mechanisms of impairments because different brain regions support different cognitive processes. Continuing the exemplar of social cognition, adults and children recruit a network of brain regions when engaging in social reasoning including bilateral temporal parietal junction (TPJ), precuneus, and medial prefrontal cortex. We have shown that this network becomes increasingly functionally specialised during early childhood and that children who perform better on behavioural Theory of Mind tasks, an indicator of reasoning about others' minds, have more functionally mature, selective responses in the right TPJ and more correlated activity between brain regions within this cortical network. If children born preterm have domain-specific atypicalities in social cognition, these atypicalities should be accompanied by atypical development in social brain regions.

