### 2.2.3 Endpoint WP3

We will define the functional and structural neural substrates of critical cognitive functions in preterm children, determine the extent to which behavioural atypicalities are domain-specific versus domain-general, and, using perinatal data, characterize factors that explain the neural bases of cognitive impairment and resilience at 5-years (WP3).

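### WP3 aims to separate domain-specific from domain-general deficits, but the protocol names no between-domain contrast and no power for one

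*Protocol*

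**What the plan says.** **Aim.** Hypothesis 3i reads "Preterm children have domain-specific delays in cognition at school age". The endpoint in section 2.2.3 is to "determine the extent to which behavioural atypicalities are domain-specific versus domain-general". Section 1.2.3 explains why imaging is used: behavioural tasks alone cannot tell the two accounts apart. It then predicts: "If children born preterm have domain-specific atypicalities in social cognition, these atypicalities should be accompanied by atypical development in social brain regions".

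**Analysis.** Section 9.2 (WP3) defines functional maturity for each region of interest. For network coherence, "inter-region correlations will be calculated as the average correlation between timecourses across ROIs within each network". Diffusion metrics are also averaged per network. The preterm-term comparisons it describes are:
- a whole-brain comparison of responses to domain-relevant and control scenes;
- an exploratory statement, "We will explore the impact of preterm birth on response time courses for attention and language, as well as social networks", followed by a permutation-based correction.

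The section then names linear and mixed-effects regression, motion and age as covariates for imaging measures, and a multiplicity rule: "When multiple statistical tests within a family are conducted, Bonferroni corrections will be applied". It does not define the family.

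**Power.** Section 9.1 (WP3) gives a detectable r of .20 for n=246 at 90% power, and n=42 and n=60 for single correlations of .48 and .40. It gives nothing for a difference between networks or domains.

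**The concern.** Specific versus general is a question about a difference of differences: is the preterm-term gap larger in one domain than in the others? Separate group comparisons do not answer it. One network reaching significance while another does not is not evidence that the two effects differ.

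The prediction in section 1.2.3 does not fill the gap. A social-specific deficit implies atypical social regions, but so does a general one. That finding therefore cannot favour either account.

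What is at stake is the central claim of WP3. If it rests on which tests cross a threshold, chance plays a large part unless the deficit is large.

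**Working it through.** **1. The protocol's own power figures (section 9.1).** Fisher z, two-sided alpha .05, 90% power: n = ((1.960 + 1.282)/atanh r)² + 3.
- r = .48 gives 41.4, so 42 (stated 42).
- r = .40 gives 61.5, so 62 (stated 60).
- n = 246 gives a detectable r of .205, and 88.5% power at r = .20.

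The stated figures are reproduced closely. All of them concern one correlation at a time.

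**2. Detectable r as a group difference.** The split of the 246 is not stated. Carrying over the 200:100 enrolment ratio gives 164:82 (assumption). With p = 2/3, d = r/√(p(1−p)(1−r²)) = .20/√(.2222 × .96) = 0.433 SD.

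**3. A purely general deficit tested network by network.** Assumptions: three networks (social, attention, language), equal standardised deficit d in each, common correlation ρ between the network statistics, and each network tested two-sided at .05/3 (critical value 2.394).
- Standard error = √(1/164 + 1/82) = 0.1353.
- At d = 0.433 the mean z is 0.433/0.1353 = 3.20, so power per network is Φ(3.20 − 2.394) = 79%.

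Simulated share of studies with one or two of the three networks significant:

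| True deficit in all three | Mixed pattern, ρ = .3 to .7 |
|---|---|
| 0.3 SD | 59% to 37% |
| 0.4 SD | 50% to 32% |
| 0.433 SD | 41% to 27% |
| 0.6 SD | 6% to 4% |

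At 0.433 SD most mixed patterns have two of three networks significant. A single isolated network occurs in about 10% to 12%. A two-degree-of-freedom group-by-network test, Σ(z − z̄)²/(1 − ρ) referred to chi-square, rejects in 5% throughout.

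**4. Is Bonferroni the cause?** At 0.433 SD and ρ = 0 the mixed-pattern rate is 50% at .05/3 and still about 29% with each network tested at .05. Separate testing is the main cause, and the correction adds to it.

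**5. Power of the interaction test.** For an excess δ in one network the noncentrality is (δ/0.1353)² × (2/3)/(1 − ρ). For δ = 0.4 and ρ = .3 this is 8.75 × 0.667/0.7 = 8.33.

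| Excess in one network | ρ = .3 | ρ = .5 | ρ = .7 |
|---|---|---|---|
| 0.4 SD | 74% | 87% | 98% |
| 0.2 SD | 23% | 31% | 49% |

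A one-degree-of-freedom contrast of the social network with the mean of the other two reaches 82%, 93% and 99% for 0.4 SD. It presupposes that social is the odd one out, so those figures do not describe the three-domain test.

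**The case against.** A reader might infer that the protocol tests each network separately at a Bonferroni level and will call a deficit specific according to which networks pass. The documents do not support that. No section states such a rule, the Bonferroni family is undefined, and the sentence on the three networks is exploratory and is followed by permutation correction. The .05/3 level is an assumption. So the error rates above are conditional on that way of reading the results.

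The mixed-effects models in section 9.2 could carry a group-by-domain term, and model terms are often left to an analysis plan, which is not at hand here. It is therefore right to say that no interaction is named, not that none is intended. But the protocol does fix an interaction for WP1, deprivation by gestational age, in the same section. For WP3, where the endpoint depends on one, it names none, and its power statement addresses a different question.

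Section 1.2.3 states only what a specific deficit would imply. It does not say that atypical social regions prove specificity. That is fair, and the attention and language networks are measured too, so the comparison domains are available. The prediction still does not discriminate. The whole-brain scene contrast bears on specificity within a domain but does not compare the three networks with each other.

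The endpoint is worded for behaviour and hypothesis 3i for cognition, while the calculation is for three imaging networks. The logic carries over to behavioural scores; the percentages were not computed for them.

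A reader might also infer that a general deficit will usually look specific. It will not: the mixed-pattern rate depends on effect size and correlation, and is about 0% at 0.8 SD.

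**Conclusion.** The concern holds in a limited form. The protocol states a specific-versus-general endpoint, names only per-region and per-network analyses, names no between-domain contrast or decision rule, and gives power only for single correlations. If specificity were read from the pattern of significant networks, a purely general deficit at the protocol's detectable effect would give a mixed pattern in about 27% to 41% of studies, against 5% with an interaction test.

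Those figures rest on the 164:82 split, equal standardised deficits, normally distributed test statistics, a common correlation of .3 to .7 and a three-network family. The documents give neither the deficit size nor the correlation. The gap in the plan does not depend on these assumptions; its numerical consequence does.

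**What to change.** In section 9.2 (WP3):
- Name a group-by-domain interaction (social, attention, language) in the mixed-effects model on standardised scores, with a child random effect, and with motion and age as covariates for the imaging measures.
- Fit the matching model to the behavioural domain scores.
- Require the interaction before claiming domain-specificity, and keep per-network contrasts as follow-up.
- State that a non-significant interaction is not proof of a general deficit.

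In section 9.1 (WP3), add the power of the two-degree-of-freedom test with the assumed split and correlations, using the last table above or updated inputs.

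The cost is wording and one power calculation, since the measures are already planned. The downside is that a modest domain-specific difference becomes harder to claim: at a 0.2 SD excess the test has less than even power at every correlation shown.
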